#### **7.1.2.1 Crossover**

Patients in the control arm will be allowed to crossover to PDR001 treatment if they have radiological progression (as per RECIST v1.1) documented by an independent central review and the investigator believes this is the best treatment option for the patient. The End of Treatment (EoT1) visit assessments should be performed as described in [Section 7.1.3](#) before a patient can receive PDR001 treatment.

Patients should receive PDR001 within 21 days of the last radiological assessment, if they have no Grade 3/4 AEs and brain metastases. Each case must be first discussed with Novartis. No other antineoplastic therapies are allowed from the time of disease progression to the time of

crossover treatment initiation and throughout PDR001 treatment. Once transitioned to PDR001 treatment, patients will attend the clinic for treatment and safety monitoring as described in [Section 7.2.2](#).

### 7.1.3 Discontinuation of study treatment

Patients may voluntarily discontinue from the study treatment for any reason at any time. If a patient decides to discontinue from the study treatment, the investigator should make a reasonable effort (e.g. telephone, e-mail, letter) to determine the primary reason for this decision and record this information in the patient's chart and on the appropriate eCRF. They may be considered discontinued if they state an intention to withdraw or fail to return for visits.

The investigator should discontinue study treatment for a given patient if, on balance, he/she believes that continuation would be detrimental to the patient's well-being.

Study treatment may be discontinued under the following circumstances:

- Adverse event
- Lost to follow-up
- Physician's decision
- Progressive disease as per irRC (not as per RECIST v1.1; patients treated with PDR001)
- Progressive disease as per RECIST v1.1 (patients treated with chemotherapy)
- Confirmed Complete response as per RECIST v1.1 (patients treated with PDR001)
- Study terminated by Novartis
- Patient/guardian decision
- Protocol deviation
- Technical problems

Study treatment must be discontinued if any of the following occur:

- Death
- Pregnancy

Patients who discontinue study treatment should undergo as soon as possible and within 14 days of the last dose of study drug or within 14 days of the decision to discontinue study treatment, an End of Treatment (EoT1) visit and then be discontinued from the study treatment (please refer to [Table 7-1](#) and [Table 7-3](#) for list of assessments to be performed).

Patients in the control arm, who switch to PDR001 treatment, should have an EoT visit (EoT2) once they are discontinued from PDR001 treatment (please refer to [Table 7-3](#) for list of assessments to be performed).

If the decision to discontinue the patient occurs at a regular scheduled visit, that visit may become the EoT visit rather than having the patient return for an additional visit. An End of Treatment Phase Disposition eCRF should be completed, giving the reason for stopping the study treatment. End of treatment/Premature withdrawal visit is not considered as the end of the study. The investigator must also contact IRT to register the patient's discontinuation from study treatment.

Patients who discontinue study treatment should not be considered discontinued from the study. They should return for the assessments indicated in [Section 7.1.5](#). If they fail to return for these assessments for unknown reasons, every effort (e.g. telephone calls, e-mail, letter) should be made to contact them as specified in [Section 7.1.8](#). If a patient discontinues study treatment, but continues study assessments, the patient remains on study until such time as he/she completes protocol criteria for ending study assessments.

Patients who transfer into another study or an alternative treatment option to continue provision of study treatment will perform the EoT procedures, but not any further study assessments.

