#### 6.1.3 Ancillary treatments (patients in PDR001 arm)

All patients randomized into the PDR001 arm, should not receive pre-medication to prevent infusion reaction before the first infusion of PDR001, in order to determine if pre-medication is necessary. If a patient experiences an infusion reaction, he/she may receive pre-medication on subsequent dosing days. The pre-medication should be chosen per institutional standard of care, at the discretion of the treating physician.

Acute allergic reactions should be treated as needed per institutional standard of care. In the event of anaphylactic/anaphylactoid reactions, this includes any therapy necessary to restore

normal cardiopulmonary status. If a patient experiences a Grade 3 anaphylactic/anaphylactoid reaction, the patient may only continue on the study following discussion with Novartis.

Patients should be treated in a facility equipped for cardiopulmonary resuscitation. Appropriate resuscitation equipment should be available at the bedside and a physician readily available.

Guidelines on management of PDR001 infusion reactions are provided in [Table 6-2](#).

The CTCAE category of “Infusion related reaction” should be used to describe PDR001 infusion reactions, unless the investigator considers another category, such as “Allergic reaction,” “Anaphylaxis,” or “Cytokine release syndrome” more appropriate in a specific situation.

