Grade 3 (> 2.0 - 5.0 x ULN) or Grade 4 (> 5.0 x ULN)	Any Grade ≥3 PDR001-related isolated amylase or lipase abnormality that is not associated with symptoms or clinical manifestations of pancreatitis does not require dose delay or discontinuation. The Novartis Medical Monitor should be consulted for such amylase or lipase abnormalities

Worst toxicity CTCAE Grade (unless otherwise specified)	Recommended dose interruption, delay and discontinuation for PDR001 during a cycle of treatment
Cardiac general	
Grade 2 or Grade 3	Dose delay for PDR001-related $\geq$ Grade 2 until resolved $\leq$ Grade 1 Discontinue for PDR001-related Grade 3 lasting $>$ 7 days
Grade 4	Discontinue for PDR001-related Grade 4
Endocrine See Appendix 4 "Endocrinopathy Management Algorithm" for additional guidance on monitoring and management of any grade events	
Grade 2 or Grade 3	Dose delay for any Grade $\geq$ 2 PDR001-related until resolved $\leq$ Grade 1 Grade 3 PDR001-related endocrinopathies adequately controlled with only physiologic hormone replacement do not require discontinuation
Grade 4	Grade 4 PDR001-related endocrinopathies, such as adrenal insufficiency, ACTH deficiency, hyper- or hypothyroidism, or glucose intolerance, which resolve or are adequately controlled with physiologic hormone replacement (corticosteroids, thyroid hormones) or glucose-controlling agents, respectively, may not require discontinuation after discussion with and approval from the Novartis Medical Monitor.
Skin Rash/photosensitivity See Appendix 4 "Skin Adverse Event Management Algorithm" for additional guidance on monitoring and management of any grade events.	
Grade 2	In presence of Grade 2 PDR001-related skin toxicity, treatment may be resumed (even if patient experience before a Grade 3 PDR001-related toxicity)
Grade 3 or Grade 4	Dose delay for PDR001-related Grade 3 until resolved $\leq$ Grade 1 Discontinue for PDR001-related Grade 3 lasting $>$ 7 days, or PDR001-related Grade 4
Stevens-Johnson syndrome (SJS), or Lyell syndrome/toxic epidermal necrolysis (TEN)	
Any Grade	Permanently discontinue study treatment.
Gastrointestinal See Appendix 4 "GI Adverse Event Management Algorithm" for additional guidance on monitoring and management of any grade events	
Diarrhea***	
Grade 2	Dose delay for PDR001-related Grade $\geq$ 2 until resolved $\leq$ Grade 1 or baseline

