### 7.2.2.5 Laboratory evaluations

All laboratory parameters assessed for safety purposes will be evaluated locally (except Cytokines, Serology and EBV test examinations that will be evaluated centrally). Refer to [Table 7-6](#) for a summary of the parameters to be evaluated.

More frequent evaluations may be performed at the investigator's discretion if medically indicated; results should be recorded as unscheduled laboratory assessments.

Novartis will be provided with a copy of the laboratory certification and tabulation of the normal ranges for each parameter required. In addition, if at any time a patient has laboratory parameters obtained from a different outside laboratory, Novartis must be provided with a copy of the certification and a tabulation of the normal ranges for that laboratory.

All females of childbearing potential will have a serum pregnancy test at screening/baseline and/or within  $\leq 72$  hours before first dose of study treatment, day 1 of each cycle and at EOT visit. A urine or serum pregnancy test should be performed every month during and at the end of the safety follow-up period. If the patient is not coming to the clinic for the safety follow-up visits, a urine or serum pregnancy test will be performed at home or at a local doctor's office monthly and the results will be communicated to the site staff. The result will be recorded only in the source documentation, not in the CRF. A positive pregnancy test requires immediate discontinuation of study treatment. In addition, refer [Section 8.3](#) for follow-up and reporting Pregnancies.

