### **8.3 Pregnancies**

To ensure patient safety, each pregnancy occurring while the patient is on study treatment must be reported to Novartis within 24 hours of learning of its occurrence. The pregnancy should be followed up to determine outcome, including spontaneous or voluntary termination, details of the birth, and the presence or absence of any birth defects, congenital abnormalities, or maternal and/or newborn complications. After the mother has provided consent, the newborn will be followed-up for 12 months.

When pregnancy occurs in a patient in the study, as general rule the study drug must be discontinued, though the patient may stay in the study and follow the assessments, if she wishes to do so. All assessments that are considered as a risk during pregnancy must not be performed. The patient may continue all other protocol assessments. In exceptional cases, such as a women responding to the lifesaving treatment, the study drug can be continued.

Pregnancy should be recorded on a Clinical Trial Pregnancy Form and reported by the investigator to the oncology Novartis CMO&PS Department. Pregnancy follow-up should be recorded on the same form and should include an assessment of the possible relationship to the investigational treatment and any pregnancy outcome. Any SAE experienced during pregnancy must be reported on the SAE Report Form.

Pregnancy outcomes should be collected for the female partners of any males who took study treatment in this study. Consent to report information regarding these pregnancy outcomes should be obtained from the mother.

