### **11.3 Informed consent procedures**

Eligible patients may only be included in the study after providing written (witnessed, where required by law or regulation), IRB/IEC/REB-approved informed consent or, if incapable of doing so, after such consent has been provided by a legally acceptable representative of the patient. In cases where the patient's representative gives consent, the patient should be informed about the study to the extent possible given his/her understanding. If the patient is capable of doing so, he/she should indicate assent by personally signing and dating the written informed consent document or a separate assent form.

Informed consent must be obtained before conducting any study-specific procedures (i.e. all of the procedures described in the protocol). The process of obtaining informed consent should be

documented in the patient source documents. The date when a patient's Informed Consent was actually obtained will be captured in their eCRFs.

Novartis will provide to investigators, in a separate document, a proposed informed consent form (ICF) that is considered appropriate for this study and complies with the ICH GCP guideline and regulatory requirements. Any changes to this ICF suggested by the investigator must be agreed to by Novartis before submission to the IRB/IEC/REB, and a copy of the approved version must be provided to the Novartis monitor after IRB/IEC/REB approval.

Women of child bearing potential should be informed that taking the study medication may involve unknown risks to the fetus if pregnancy were to occur during the study and agree that in order to participate in the study they must adhere to the contraception requirement for the duration of the study. If there is any question that the patient will not reliably comply, they should not be entered in the study.

[REDACTED]

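### Two PDR001 stop rules conflict in the current protocol: pregnancy (7.1.3 and 7.2.2.5 against 8.3) and Grade 3 anaphylaxis (6.1.3 against Table 6-2)

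*Protocol*

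**What the plan says.** **Pregnancy.** Protocol 7.1.3 has two lists. The first gives circumstances in which treatment may be stopped, and adverse events are among them. The second opens with "Study treatment must be discontinued if any of the following occur" and has two entries, death and pregnancy. Section 7.2.2.5 adds: "A positive pregnancy test requires immediate discontinuation of study treatment". Its next sentence sends the reader to 8.3, but only for follow-up and reporting. Section 8.3 says: "When pregnancy occurs in a patient in the study, as general rule the study drug must be discontinued". Later in the same paragraph it says: "In exceptional cases, such as a women responding to the lifesaving treatment, the study drug can be continued".

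**Grade 3 anaphylaxis.** Section 6.1.3 says that after a Grade 3 anaphylactic or anaphylactoid reaction "the patient may only continue on the study following discussion with Novartis". The same section says "Guidelines on management of PDR001 infusion reactions are provided in" Table 6-2. In that table, the Grade 3 or 4 row for infusion or hypersensitivity reactions says to stop the infusion and discontinue the patient. The table's action column is headed as recommended.

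**Liver.** Table 6-2 discontinues for PDR001-related Grade 3 or 4 AST/ALT, where Grade 3 starts above 5 x ULN. A footnote to the hepatic algorithm in Appendix 4 mentions delay in place of discontinuation when AST/ALT is at most 8 x ULN and total bilirubin at most 5 x ULN.

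**The concern.** A site that opens one page of the protocol can keep on drug a patient whom another page takes off it. A pregnant patient who is responding is stopped at once under 7.1.3 and 7.2.2.5 but may stay on PDR001 under 8.3. Section 11.3, meanwhile, requires women to be told that "taking the study medication may involve unknown risks to the fetus if pregnancy were to occur during the study". A patient with a Grade 3 anaphylactic reaction is stopped under Table 6-2 but may be re-exposed under 6.1.3.

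Pregnancy also raises a classification problem. SAP 2.4 tabulates deviations, including a category for patients not discontinued after meeting withdrawal criteria. A pregnant patient kept on drug under 8.3 complies with that section and violates the other two, so she cannot be classified consistently.

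**Working it through.** The plan gives no figure to reproduce for either conflict. The check sets the passages side by side.

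**1. Pregnancy**

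| Place | Rule | Exception | Approver |
|---|---|---|---|
| 7.1.3 | must stop | none | not applicable |
| 7.2.2.5 | stop immediately on a positive test | none; pointer to 8.3 for follow-up and reporting | not applicable |
| 8.3 | stop as a general rule | exceptional cases may continue | not named |

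- Could the difference in terms, treatment in 7.1.3 and 7.2.2.5 but drug in 8.3, explain it? No. Protocol 6.1 counts PDR001 as a study treatment and SAP 2.1.1 defines study drug as PDR001, so both rules reach it.
- Could the pointer in 7.2.2.5 import the exception? No. It covers what to do after a pregnancy and how to report it, not whether to stop.
- Is the mandatory wording in 7.1.3 an accident? Unlikely. The rationale for Amendment 03 says the section was clarified to separate possible from mandatory reasons for stopping.
- Does the protocol name an approver when it wants a controlled exception? In at least one place, yes. The Grade 4 endocrinopathy row of Table 6-2 says treatment "may not require discontinuation after discussion with and approval from the Novartis Medical Monitor". Section 8.3 has no equivalent.

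**2. Grade 3 anaphylaxis**

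- Does the Table 6-2 row cover anaphylaxis? Yes on the natural reading. The row names hypersensitivity reactions, and 6.1.3 lists anaphylaxis among the CTCAE categories that may describe a PDR001 infusion reaction.
- At Grade 4 there is no clash, because the 6.1.3 sentence concerns Grade 3 only.
- At Grade 3 the row discontinues without exception, 6.1.3 permits continuation after sponsor discussion, and neither mentions the other's outcome.
- Both texts speak of the study rather than study treatment. I read both as treatment, because 6.1.2 and 7.1.3 say that stopping treatment is not leaving the study.

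**3. Liver**

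Table 6-2 Grade 3 AST/ALT is above 5.0 and up to 20.0 x ULN. The footnote reaches 8 x ULN. The overlap is:

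(5.0, 20.0] ∩ (0, 8] = above 5.0 up to 8.0 x ULN, with bilirubin at most 5 x ULN.

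Within that range the documents largely settle precedence. Section 6.2.3 says to interrupt treatment for a related Grade 3 event and leaves departures from that to Table 6-2. The table cites Appendix 4 as additional guidance. The appendix describes itself as general guidance for all immuno-oncology agents. The footnote also qualifies a figure that is not shown in the text available, so the box it modifies cannot be seen.

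**The case against.** The best defence is that only the pregnancy wording matters. For anaphylaxis, Table 6-2 recommends rather than mandates, 7.1.3 puts adverse events under the reasons that *may* lead to stopping, and 6.1.3 is the more specific text and allows continuation only after sponsor contact. All of that is correct and it makes the second conflict softer. It does not remove it: a site reading the table alone would stop, a site reading 6.1.3 alone would telephone the sponsor, and 6.1.3 itself sends the reader to the table.

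For pregnancy, the defence can point to the cross-reference in 7.2.2.5 and to the 24-hour reporting duty in 8.3, which means the sponsor would learn of every on-treatment pregnancy. Reporting is not approval, and 8.3 makes continuation conditional on neither.

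Four stronger readings are tempting, and the documents do not support them:

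- *That the liver footnote is a third conflicting stop rule.* On the natural reading Table 6-2 already governs. What is missing is a sentence saying so.
- *That a site following 6.1.3 departs from mandatory text and so breaches Section 12, which allows no authorised deviations.* The opposing text is a recommendation, and 6.1.3 is itself an express protocol provision.
- *That 6.1.3 allows uncontrolled re-exposure.* Sponsor discussion is a precondition.
- *That the stop rules cost follow-up or disturb the PFS analysis.* Sections 6.1.2, 7.1.3, 7.1.6 and 7.1.7 keep patients who stop for an adverse event under follow-up.

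**Conclusion.** Two stop rules are inconsistent as written. Pregnancy is the firm one: two unqualified requirements to stop stand against a softened rule with an open-ended exception and no approver. Grade 3 anaphylaxis is a real but milder mismatch between a recommended stop and a sponsor-gated permission to continue. The liver item is a precedence clarification.

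The size is small. Of 122 randomised patients, 82 went to PDR001. On 21 May 2019, 12 patients were still receiving it: 11 randomised to it and one crossover. The documents give no rates for pregnancy or anaphylaxis, so I do not estimate a number affected. No endpoint, power or error rate changes. The case for correcting the text is patient safety and consistent conduct.

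The anaphylaxis conclusion assumes that anaphylaxis falls within the infusion/hypersensitivity row and that study means study treatment in both places.

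**What to change.** **Pregnancy.** By default, delete both the general-rule qualifier and the exceptional-case sentence from 8.3, so that it matches 7.1.3 and 7.2.2.5. Deleting the exception alone would leave the softened wording in place. If the sponsor intends the exception, cite it in 7.1.3 and 7.2.2.5 and name who approves it.

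**Grade 3 anaphylaxis.** Make 6.1.3 and Table 6-2 agree. By default, delete the continuation sentence in 6.1.3. Otherwise, write a sponsor-approved exception for Grade 3 into the Table 6-2 row.

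**Liver, clarification only.** Add one sentence stating that Table 6-2 governs over the Appendix 4 algorithms.

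**Cost.** The default route removes one phrase and two sentences and adds one sentence. Under Section 12.1 it needs a written amendment approved by the sponsor and the IRB/IEC/REB, and by Health Authorities where required. It adds no procedure, visit or data item and leaves the SAP unchanged.

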#### **7.1.4 Withdrawal of consent**

Patients may voluntarily withdraw consent to participate in the study for any reason at any time. Withdrawal of consent occurs only when a patient does not want to participate in the study any longer, and does not allow further collection of personal data.

If a patient withdraws consent, the investigator should make a reasonable effort (e.g. telephone calls, e-mail, letter) to determine the primary reason for this decision and record this information.

Study treatment must be discontinued and no further assessments conducted, and the data that would have been collected at subsequent visits will be considered missing.

Further attempts to contact the patient are not allowed unless safety findings require communication or follow up.

All efforts should be made to complete the assessments prior to study withdrawal. A final evaluation at the time of the subject's study withdrawal should be made as detailed in the assessment table.

Novartis will continue to keep and use collected study information (including any data resulting from the analysis of a subject's samples until their time of withdrawal) according to applicable law.

For US and Japan: All biological samples not yet analyzed at the time of withdrawal may still be used for further testing/analysis in accordance with the terms of this protocol and of the informed consent form.

For EU and RoW: All biological samples not yet analyzed at the time of withdrawal will no longer be used, unless permitted by applicable law. They will be stored according to applicable legal requirements.

#### **7.1.5 Follow up for safety evaluations**

All patients in the PDR001 treatment arm must have safety evaluations for 150 days after the last dose of study treatment. Patient in the Chemotherapy arm must have safety evaluations for 30 days after the last dose of study treatment.

Patients in the control arm who crossover are not required to have a 30-day safety follow-up performed and can crossover as soon as the End of Treatment (EoT1) visit is complete. Once patients discontinue PDR001 crossover treatment, safety follow-up must be performed for 150 days after the last dose of PDR001.

The evaluations can be done either by telephone call or visit for the 30-, 90-, and 150-day safety follow-up visits for the PDR001 arm and crossover patients. Concomitant medications will be collected until the 30- day safety follow-up has been completed or the start of a new antineoplastic therapy, whichever occurs first. A PK and immunogenicity sample should be collected at 150 days for PDR001 arm patients only, as described in [Section 7.2.3](#). If the 150-day safety evaluation is conducted by phone, samples do not need to be collected.

Data collected during the Safety follow up period should be added to the Adverse Events eCRF, Concomitant Medications eCRF, Antineoplastic therapies since discontinuation of study drug eCRF (including tumor directed surgical procedures) and Unscheduled blood collection for PK and IG eCRFs. All AEs suspected to be related to study treatment should be followed weekly, or as clinically indicated, until resolution or stabilization. For female patients of child bearing potential, pregnancy tests will be performed as outlined in [Section 7.2.2.5](#).

The safety follow-up will not be performed for patients who transfer to another study or to an alternative treatment option to continue provision of study treatment.

